Along with decrease beta-cell function, youth with type 2 diabetes become resistance to pharmacological mono-therapy (metformin or rosiglitazone) and lifestyle intervention such as change in diet and physical activity. Due to these limiting factors, once a pre-diabetic child or adolescent develops type 2 diabetes, it is considered irreversible (Zeitler et al, 2012.) Given this, the focus is on early prevention of on-set pre-diabetes or type 2 diabetes among the obese youth population. Early lifestyle prevention and intervention programs consist of changing diet, physical activity and lifestyle habits (i.e taking the stairs instead of the elevator) through education. A number research study-programs have shown promising results in regards to diabetes prevention such as: 42% reduction of whole body insulin sensitivity, a two- fold greater change in body fat than body weight, increase lean body mass, and normalized fasting, two-hour plasma blood glucose levels, and decrease LDL cholesterol levels (Shaw, 2009, Wadden, 2012.)

In addition to the physical and metabolic impact of obesity, research supports the relationship between obesity, mental health, and health behaviors. Generally, overweight and obese youth have increased mental health concerns compared to their normal weight peers (Sinha, 2002.) Specifically, obesity has been linked to presence of depression, anxiety, attention deficit hyperactivity disorder, and conduct disorder among children (Halfon, 2013, Puder, 2010.) Difficulty coping with stress and decreased self-esteem are also associated with obesity (BeLue, 2009.) Studies have also shown that individuals, adults and youth, with type 2 diabetes have decreased cognitive functioning including mental processing speed, flexibility, memory, and learning (Puder, 2010.) Physical activity participation has been linked with improved academic performance, mental health, and cognitive function (Hillman, 2008.) Despite these findings, the best treatment or weight management for childhood obesity is still uncertain. A few studies have examined the cumulative impact of improving physical activity, fitness, nutrition, and overall health behaviors in children. The specific aims of this research project are to:

- 1) Examine the change of health status of youth participants over time as a result of the 12-month (16 weekly, 3 biweekly, and 6-monthly session) ISC intervention through the evaluation of metabolic, physical fitness, and health habit parameters
- 2) Examine the change of health status of parent participants over time as a result of the 12-month (16 weekly, 3 biweekly, and 6-monthly session) DPP adult sessions through the evaluation of metabolic, physical fitness, and health habit parameters.
- 3) Examine the differences over time in metabolic, physical fitness, and health habit parameters among participants in the ISC group versus those in educational control group.

23.0 (1200) Site and Research Procedure Information

*Please list all sites and research procedures that will occur at each site. Research Site(s): If any of the following activities are being done, then include the site(s) below: identification of participants through review of their medical records; recruitment of participants; consent of participants; performance of screening procedures; interventions or interactions with participants; follow-up visits; collection of private information about participants; specimen storage; etc. Note: If any

activities are being conducted at any of the following: CRC, Methodist/Le Bonheur, Regional One Health, or University Clinical Health, review the corresponding institution's guidelines prior to submitting your application. The website listing the institution's point of contact is posted under the "Ouestion Mark" icon to the right.

Site Name and Address		Additional Site Information include suite #	
Institution: Other		YMCA [name]	Program staff training will be conducted at this site.
Institution: University of Tennessee - Health Science Center		CFRI-[name]	All consenting, data collection, data storage, data input and analysis will be at this site.
		Gaisman Community Center, [name]	ISC and WSC programs will be in held at this site.

23.2	* Is this a multicenter study/project (one that is conducted across many institutions in the U.S. or in the world and usually
	run by one sponsor)? Select "Not Applicable" if you are using a HUD, or engaging in treatment use of an unapproved
	drug/biologic or device, emergency use of an unapproved drug/biologic or device, or compassionate use of an unapproved
	device.

🔘 Yes. This is a multicenter study/proje	О.	Yes.	This	is a	multicenter	study	/projec
------------------------------------------	----	------	------	------	-------------	-------	---------

- No. This is NOT a multicenter study/project.
- Not Applicable.

23.3 * Please state the intended number of multicenter sites in aggregate; state "0" if this is not a multicenter study (one that is conducted across many institutions in the U.S. or in the world and usually run by one sponsor).

24.0 (1400) Subject Population

24.1 Please state the anticipated number and age range of the subjects to be studied.

* Number of subjects to be accrued locally [This is the total number of subjects you expect to accrue (consent), including anticipated screen failures and withdrawals. For studies with pregnant women where information will be collected about both the mother and fetus/baby, both should be counted as subjects. For studies that are requesting an alteration or waiver of consent, subjects are considered accrued at the time ANY study interventions are performed, including medical record abstraction.]:

100

Overall number of subjects for sponsored multi-center studies [This is the total number of subjects that the protocol states will participate in the study across all centers.]:

* Age range of subjects to be accrued locally:

7-15 and 18+

25.0 (1488) Vulnerable Subjects

25.1 * Does your study require the inclusion of (i.e., are you targeting) any of the following categories of vulnerable subjects?

Clicck	хан спас арргу.	
☐ Children	(0-17 years) Who Are Not Wards of the State	
	(0-17 years) Who Are Wards of the State	
	It Females and Their Fetuses	
	es Who Are Nonviable or of Uncertain Viability	
Prisoner		
	mentally Disabled Persons (Who Are Not Institutionalized)	
	mentally Disabled Persons Who Are Institutionalized	
	Who Are Mentally III (But Who Are Not Institutionalized as Mentally III)	
	Who Are Institutionalized as Mentally Ill	
	s of a School Associated With This Project	
	ees of an Institution/Agency Associated With This Project	
	ulnerable Population Not Identified Above	
№ Not App	licable Subjects Not Classified as Vulnerable	
_	t any of the following categories of vulnerable subjects be incidentally included in your study, even gh their inclusion is not necessary? Check all that apply.	
Children	(0-17 years) Who Are Not Wards of the State	
	(0-17 years) Who Are Wards of the State	
Pregnan	t Females and Their Fetuses	
□ Neonate	es Who Are Nonviable or of Uncertain Viability	
Prisoner	rs ·	
Develop	mentally Disabled Persons (who are not institutionalized)	
Develop	mentally Disabled Persons Who Are Institutionalized	
Persons	Who Are Mentally III (but who are not institutionalized as mentally ill)	
Persons	Who Are Institutionalized as Mentally III	
☐ Students	s of a School Associated with this Project	
☐ Employe	ees of an Institution/Agency Associated with this Project	
Dl1-:		
Please explai	in how a certain category of vulnerable subjects might be incidentally included:	
26.0 (14	194) Study/Project Duration	
26.1 * Wha	at is the anticipated duration of a single subject's participation in the study/project?	
	ar is the material and money a surged of participation in the setting, projects	
1 year		
26.2 * How	v long will the entire study last locally, including time for data analysis?	
5 years		
27.0 (15	500) Inclusion Exclusion Criteria	
27.1 Identi	fy inclusion criteria.	
Order		
Number	Criteria	
1	1) Ages 7-15	
	Parent Inclusion Criteria: 18 and older	

1	
2	2) Prediabetes-A1C 5.7-6.4% ${f or}$ BMI of an 85th percentile or above ${f or}$ a grandparent /parent with diabetes
2	Parent Inclusion Criteria: at least one child enrolled in ISC
3	3) Able to participate in physical activity
3	Parent Inclusion Criteria: Able to do physical activity
4	4) Parent enrolls in the adult DPP

27.2 Identify exclusion criteria.

Order Number	Criteria
1	1) pregnant females
1	Parent Exclusion Criteria: those with mental disorder (e.g. depression, ADHD, etc.) and/or severe mental illness which requires immediate treatment (e.g., active psychotic episode)
2	2) those with mental disorder (e.g. depression, ADHD, etc.) and/or severe mental illness which requires immediate treatment (e.g., active psychotic episode)
3	3) medications that would interfere with testing results (eg. metformin, insulin)
3	Parent Exclusion Criteria: medications that would interfere with testing results (eg. metformin, insulin)

28.0 (1600) Subject Selection and Recruitment					
28.1 * How will subjects be selected?					
* Subjects identified through medical record screening					
⊙ Yes ○ No					
* Contact by investigator with his/her patients in the clinical setting					
⊙ Yes ○ No					
* Referral from non-investigator practitioner					
⊙ Yes C No					
* Subjects recruited from among students and/or employees					
O Yes ⊙ No					
* Telephone pre-screening					

* Website pre-screening	
C Yes No	
* Advertising	
* Other	
O Yes O No	
28.2 * Recruitment Materials	
At the end of this application, you are required to attach all recruitment materials which you intend to use for this study /project.	
 No recruitment materials will be used in this research. Recruitment materials to be used in this research will be attached at the end of this application. Recruitment materials will be submitted at a later date. 	
* Describe how/where EACH of your recruitment materials (by name) will be used, in the text box below; e.g., on a website, sent to an email list, posted on campus, in a newspaper, etc.	
Flyers and project information that will be posted on campus and throughout the community.	
29.0 (1710) Study/Project Procedures	
29.1 * Describe the procedures that will be performed to determine whether prospective subjects satisfy inclusion /exclusion criteria for study/project participation.	
* Medical Record Review should be included as a procedure if it is used to determine whether prospective subjects satisfy the criteria for study/project participation.	
Prospective subjects will be screened by a research staff personnel or screened by a health professional that is referring the participant. They will determine whether they qualify for the program if they meet the inclusion/exclusion criteria.	
29.2 * Do the study/project procedures involve administration of a drug, device or other intervention to determine its efficacy, safety, and/or tolerability for treatment purposes?	
 Yes. The study/project procedures involve administration of a drug, device or other intervention to determine its efficacy, safety, and/or tolerability for treatment purposes. No. The study/project procedures DO NOT involve administration of a drug, device or other intervention to determine its efficacy, safety, and/or tolerability for treatment purposes. 	
30.0 (1730) Procedures other than Treatments	

30.1 * Describe all procedures, other than treatments, that will be performed.

For studies/projects that involve multiple study/project visits, specify the timing of each visit, and in chronological order, list what will be done at each visit.

Click on "Add a new row" to list each procedure of each visit.

If you do not wish to use the table, click on the Text Editor and type in the information (specify the timing of each visit and list in chronological order, using bullet points, what will be done at each visit).

Also use the Text Editor to further describe any procedures that are not self-explanatory.

Visit Name	Visit Timing	Procedure
Consent, registration	1-2 hours	Consenting
Pre-evaluation	1-2 hours	Pre-evaluation see below for details
Mid-evaluation	1-2 hours	Mid-evaluationsee below for details
post-evaluation (3 month)	1-2 hours	post-evaluationsee below for details

Consent, register participants, questionnaire completion

• The first visit will be for program registration and consenting at the Gaisman Community Center. Research staff will consent parents, assent children, and sit face-to-face with the parent and child to complete the Healthy Habits and mental health questionnaire. This will take about 1-2 hours to complete.

Pre-Evaluation

• All physical activity, physical fitness, and health measures described will be collected at the Gaisman Community Center. This will take about 1-2 hours to complete. The drop-off/pick-up home visit appointments will also be scheduled in order to collect physical activity data described in the health behaviors measures. The child will be asked to wear the activity monitor for 7-days hours. The drop-off home will take 30 minutes. The pick-up home visit will take 30 minutes. Both home visits will add up to 60 minutes to complete.

Mid-Evaluation

• All physical activity, physical fitness, and health measures (except the blood glucose and cholesterol) described above will be collected at the Gaisman Community Center. This will take about 2 hours to complete.

Post-Evaluation

• Research staff will sit face-to-face with the parent and child to complete the Healthy Habits and mental health questionnaire. All physical activity, physical fitness, and health measures described above will be collected. This will take about 1-2 hours to complete at the Gaisman Community Center. The drop-off/pick-up home visit appointments will also be scheduled in order to collect physical activity data described in the health behaviors measures. The child will be asked to wear the activity monitor for 7-days. The drop-off home will take 30 minutes. The pick-up home visit will take 30 minutes. Both home visits will add up to 60 minutes to complete.

31.0 (1731) Incidental Findings

31.1 * How will abnormal incidental findings be handled?

- The subject will be referred for follow-up to his/her primary care physician.
- The study doctor will provide follow up for the abnormal finding.
- Other
- O Not Applicable; incidental findings are not expected in this project.

32.	0 (1733) Creation of Specimen & Data Repositories/Registries	
32.:	* Does this study include creating a specimen repository or a data registry/repository? A repository is established when there is a plan to make stored data and/or specimens available for later use in other research studies.	being
	Yes No	
33.	0 (1734) Use of Other Data/Specimen Repositories	
33.:	1 * Will this project/study involve using data/specimens from other repositories?	
	Yes No	
34.	0 (1735) Discontinuation, Endpoints, Analyses	
34.:	1 * Describe the criteria for discontinuation of treatment and withdrawal of the subject from the study/project.	
N/A	A	
34.2	2 * Describe the endpoints or outcomes being assessed in the study/project, such as efficacy and safety endpoints.	
Ch Ba: Ch Ba: (Ti	tcome Measures: ange Over Time: Intervention seline (Time: 0) by changes over time (mid-intervention (Time: 1), and post-intervention (Time: 2)) ange Over Time: Maintenance seline (Time: 0) by changes over time (3-months out (Time: 3), 6 months out (Time: 4), 9 months out me: 5), 12 months out (Time: 6) st-intervention (Time: 2) by changes over time (3-months out (Time: 3), 6 months out (Time: 4), 9 onths out (Time: 5), 12 months out (Time: 6))	
34 1	3 * Describe the statistical analysis that will be used.	
J-7	Describe the statistical analysis that will be used.	
Phyto how physical ph	mary Predictors: ysical Activity: An accelerometer (Computer Science and Applications, Inc., Shalimar, FL), will be used assess physical activity. To ensure good reliability of devices used, children and parents will be taught w to use the accelerometers and reminded to wear them via a phone call. Self-report measures of ysical activity and sedentary habits will also be obtained. ysical fitness (cardiorespiratory, muscular strength and endurance, and motor skills): The fitness ttery will include the American Thoracic Society six-minute Walk Endurance Test (aerobic fitness) while onitoring pulse oximeter (blood oxygen), Jamar plus handgrip dynamometer (grip strength), MicroFET-2 indheld dynamometer (maximal isometric strength), sit-and-reach box (lower body flexibility), 30-foot uttle run (agility), and Bruininks-Oseretsky Test of Motor Proficiency (fine and gross motor control	

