- 2) Examine the change of health status of parent participants over time as a result of the 12-month (16 weekly, 3 biweekly, and 6-monthly session) DPP adult sessions through the evaluation of metabolic, physical fitness, and health habit parameters.

3. Study/Project Population,

Potential subjects and their parents will be informed of the study through flyers, community events, and physician referrals. Flyers will be distributed/posted at all YMCA sites and physician offices and clinics, throughout Memphis.

Inclusion criteria for youth participants will include:

- 1) Between 7-15 years-old
- 2) Hemoglobin A1C 5.7-6.4% or BMI \geq 85th percentile, parent **or** grandparent with pre/type II Diabetes
- 3) Able to participate in physical activity
- 4) Parent or caregiver participation

Exclusion criteria for youth participants will include:

- 1) Pregnant females
- 2) Those with mental health illness (e.g. depression, ADHD, etc.)
- 3) Medications that would interfere with testing results (e.g. metformin, insulin)

Inclusion criteria for parent participants will include:

- 1) ≥18 years-old
- 2) At least one child enrolled in ISC
- 3) Able to participate in physical activity

Exclusion criteria for parent participants will include:

- 1) Those with mental health illness (e.g. depression, ADHD, etc.)
- 2) Medications that would interfere with testing results (e.g. metformin, insulin).

Inclusion and exclusion criteria will be assessed via parent and child self/physician referral form. The UTHSC/LBCH subcommittee will approve all procedures for the Use and Protection of Human Subjects. ISC and control group participants will be assigned on a fist come first serve basis.

Consenting and Questionnaires:

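### Pregnancy is an exclusion for youth but not for parents, so if a parent is pregnant or recently post-partum at an evaluation, the resulting change would be read as a programme effect in Aim 2

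*Combined protocol and SAP*

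**What the plan says.** **Eligibility, section 21.1 item 3.** The first youth exclusion is "1) Pregnant females". The parent list, headed "Exclusion criteria for parent participants will include", has two entries: mental illness and medication that would disturb the tests. Under "Inclusion criteria for parent participants will include" the plan asks for adult age, a child in the club and the ability to be physically active. None of these screens out pregnancy.

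**Eligibility, section 27.2.** The table has one pregnancy row, "1) pregnant females", with no parent label. The rows that apply to parents carry their own label, as in "Parent Exclusion Criteria: medications that would interfere with testing results (eg. metformin, insulin". They cover mental disorder and medication only.

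**Aim 2, section 21.1 item 2.** The aim is to "Examine the change of health status of parent participants over time as a result of the 12-month" "DPP adult sessions through the evaluation of metabolic, physical fitness, and health habit parameters". Section 21.1 items 5 and 6 define the metabolic measures as weight, percent body fat, BMI, sagittal abdominal height, a tape measure of central obesity, blood pressure, heart rate, A1C and lipids.

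**Design and analysis.** Section 21.1 item 4 describes one intervention group without a control and six evaluations over the year. The covariates in section 21.1 item 6 and section 34.3 include no pregnancy term. Section 34.1, on withdrawal, is answered as not applicable.

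**The concern.** The plan already removes parents whose medication would disturb the measurements, so it means to keep known sources of disturbance out of the parent data. Pregnancy is another such source for most of the metabolic measures. It is excluded at ages 7 to 15 and left open for adults, in whom it is more likely.

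Aim 2 is a within-parent change with no comparator. Change from any cause between two evaluations therefore enters the estimate. A parent who becomes pregnant, is pregnant at entry, or is recently post-partum would contribute change that has nothing to do with the sessions. In a small group, one or two such values can move the mean and widen its interval.

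**Working it through.** **1. Is there a rule anywhere?** The places where one could stand are:

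| Place | Pregnancy in youth | Pregnancy in parents |
|---|---|---|
| 21.1 item 3, exclusions | listed | not listed |
| 27.2, exclusions | unlabelled row | not in the parent-labelled rows |
| 21.1 item 6 and 34.3, covariates | none | none |
| 34.1, withdrawal | not applicable | not applicable |

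No section tells the team to record pregnancy in parents, exclude it, or handle affected values.

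**2. Is there a figure to reproduce?** No. Section 24.1 gives 100 subjects, youth and adults together and including screen failures and withdrawals. It gives no split and no derivation. The plan states no SD or expected change. What follows shows scale only, and every input is an assumption.

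**3. Main illustration.** Assume n = 50 parents, of whom k = 1 or 2 become pregnant with an observed gain g of 8 to 14 kg. The others have mean change -2 kg and SD 4 kg. An affected parent differs from the others by g + 2.

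- Shift in mean = k(g + 2)/n. Low: 1 × 10/50 = 0.20 kg. High: 2 × 16/50 = 0.64 kg.
- Observed mean: -1.80 to -1.36 kg instead of -2 kg, so 10% to 32% of the assumed change is lost.
- SD = √[16(1 − k/n) + (k/n)(1 − k/n)(g + 2)²], treating the gain as identical in affected parents.
  - Low: √(15.68 + 1.96) = 4.2 kg.
  - High: √(15.36 + 9.83) = 5.0 kg.
- Mean divided by its standard error:
  - no pregnancy: 2/(4/√50) = 3.5
  - low case: 1.80/(4.2/√50) = 3.0
  - high case: 1.36/(5.0/√50) = 1.9

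**4. Opposite direction.** A parent who is pregnant at baseline and delivers before a later evaluation may weigh less than at entry. If one or two such parents showed an observed loss of 8 to 14 kg (also assumed), the shift would run from −1 × 6/50 = −0.12 kg to −2 × 12/50 = −0.48 kg. That would look like programme benefit.

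**5. Wider range.** Take 30 to 50 parents, 1 to 3 affected, a pregnancy-related difference of 5 to 15 kg from the others, and SD 5 kg. The shift runs from 1 × 5/50 = 0.10 kg to 3 × 15/30 = 1.50 kg. In standard errors that is 0.14 (0.10/0.71) to 1.64 (1.50/0.91).

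**6. Chance of at least one affected parent.** This is 1 − (1 − p)ⁿ, where p is the share of parents pregnant at some point in the year. For p from 1% to 10% it is 26% to 96% with 30 parents and 39% to 99% with 50.

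**The case against.** **The effect is conditional.** A reader might infer that pregnancy-related change will be part of the Aim 2 result. The documents do not support that. They give no expected number of pregnancies and no sex mix among parents. Without an affected parent there is no bias, and at the low end of the assumptions the shift is a fraction of a standard error. This stands.

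**The group size is not stated.** A reader might take 100 subjects to mean 50 parents. Section 24.1 gives no split, and section 21.1 item 3 allows more than one child per family. This stands, so 50 is only an assumption.

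**The direction is not fixed.** A reader might infer that the omission always hides benefit. Step 4 shows that it can also create apparent benefit.

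**Parent measurements are not listed separately.** The procedures are written mainly for the child; the blood pressure cuff, for instance, is child-sized. That parents have the same metabolic measures is inferred from Aim 2, which names the same domains. The inference is reasonable, but it remains one.

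**The pregnancy row in section 27.2 could cover everyone.** It carries no label. However, youth rows in that table are unlabelled and parent rows are labelled, and section 21.1 item 3 puts pregnancy under youth only. This objection does not stand.

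**A control group may exist.** Section 22.1 adds an aim that compares the club with an educational control, which conflicts with the design in section 21.1 item 4. That aim would not alter Aim 2, which remains a change within parents.

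**Conclusion.** The omission is real and appears in both eligibility sections. If a parent is pregnant or recently post-partum at an evaluation, the plan as written would count the related change as an effect of the adult sessions. Under the assumptions of step 3, mean weight change moves by +0.20 to +0.64 kg against an assumed -2 kg, and the SD rises from 4 to about 4.2 to 5.0 kg. In the upper case this could decide whether the change is called significant at conventional levels; in the lower case it would hardly matter. The bias can take either sign, and nothing in the plan bounds it. This is a low-cost improvement to Aim 2, not a fault that undermines the study. It does not bear on the youth aim.

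A reader might conclude that pregnant parents should be barred from enrolling. The point does not support that. It concerns which values enter the Aim 2 analysis, and an enrolment bar could cost a child a place, because section 27.1 makes the parent's enrolment in the adult programme a condition for the child.

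**What to change.** - **Record.** Ask and record parent pregnancy status, including recent delivery, at each evaluation.
- **Analysis-set rule.** Exclude parents who are pregnant at baseline from the Aim 2 metabolic and body-composition analysis. Set values affected by a later pregnancy to missing. Define in advance which post-partum visits count as affected, including at baseline. State this in the analysis section, not in the parent eligibility criteria.
- **Model.** Analyse each parent measure with a likelihood-based mixed model that keeps the parent's unaffected visits. The repeated measures ANOVA named in section 21.1 item 6 and section 34.3 is not clearly such a model. If it were run on complete cases, one missing visit would drop the whole parent.
- **Sensitivity.** Repeat the analysis with all values included, and report how many parents and visits the rule affected.

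**Cost.** One extra question per evaluation, a short paragraph in the analysis plan and the loss of a few parent values. The estimate then describes change outside pregnancy, which should be said in the report. The parent's attendance and the child's eligibility are unaffected.
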